7.3 Post-Treatment Period

Subjects will return to the study site approximately 30 days after their last dose of study drug to complete end-of-study assessments if they progressed on study while still on active treatment. If the subject is already off treatment at the time of disease progression, by either scan or exam, then the end of study assessments may occur anytime within 30 days of documented disease progression. Laboratory and physical examinations will be performed. Remaining study

treatment will be returned by the subject, and treatment compliance will be documented. Additional follow-up will occur for subjects with AEs related to study treatment that are ongoing at the time of this visit, and for subjects with SAEs related to study treatment that occur after the time of this visit. Patients who complete treatment will be followed as in schedule Table 7-1. Patients who are beyond 2 years from last treatment on study will be monitored for progression free survival and overall survival every 6 months via chart view or phone contact for total of 5 years from starting the study treatment. Management including but not limited to laboratory assessment, history/physical examination, imaging studies will be at the discretion of the treating provider.

Patients who come off treatment for progression should be followed for overall survival for up to 5 years from the start of study treatment. Follow up contact for survival should be performed every 6 months by chart review or phone call, unless the patient has withdrawn consent from the trial.

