7.2 Treatment Period

During the Treatment Period subjects will receive nivolumab, ipilimumab and cabozantinib until either disease progression, the occurrence of unacceptable drug-related toxicity or for other reason(s) for subject withdrawal as described in Section 5.2. Treatment will continue for up to 2 years unless there is disease progression, drug intolerance or other reason for discontinuation discussed with the principal investigator (PI). Patients with ongoing complete or partial response may discontinue therapy after 1 year on treatment at the discretion of the treating investigator. Subjects should be instructed to immediately inform the PI/sub-I of any AEs. Subjects experiencing seizures, dizziness, sleepiness, or other symptoms that could influence alertness or coordination should be advised not to drive or operate other heavy machinery.

The following schedule of assessments applies to all subjects (

Table 7-1). More frequent assessments should be obtained if clinically indicated.

Table 7-1: Study Assessments

		Schedule											
		Nivo-Ipi-Cabo combination treatment								Nivo-Cabo treatment		Off treatment but not progressed ⁹	At progression
Cycle Week	Baseline Screening	1	1	4	4	7	7	10	10	13	Q4weeks (weeks 17-105)	Q12 weeks (+/- 4 weeks)	30 day follow up visit
Day of cycle (+/- 3 days)	-14 to 0	1	8	1	8	1	8	1	8	1	1	1	1
Nivolumab dosing q3weeks		X		X		X		X		X	X		
Ipilimumab dosing q3weeks		X		X		X		X					
Cabozantinib dosing continuous		X		X		X		X		X	X		
Medication compliance		X		X		X		X		X	X		
Prior and concomitant medications	X	X		X		X		X		X	X	X	X
Baseline tissue collection ¹	X												
Baseline stool collection		X ⁷											
Physical exam	X	X		X		X		X		X	X	X	X
Vital signs	X	X		X		X		X		X	X	X	X
ECOG PS	X	X		X		X		X		X	X	X	X
Height	X												
Weight	X	X		X		X		X		X	X	X	X
Labs ²	X	X	X	X	X	X	X	X	X	X	X	X	X
Pregnancy test ³	X	X		X		X		X		X	X	X	
12 Lead EKG	X	X		X		X		X		X	X		
Tumor imaging assessments ⁴	X ⁴									X	X ⁶	X ⁶	
Adverse event assessment	X	X		X		X		X		X	X		X
Tumor biopsy ⁵										X			X
Research blood collection ⁸		X		X		X		X					X

1. Baseline tumor collection can be archived specimen if no intervening systemic therapy or fresh biopsy (core needle biopsy, punch biopsy or incisional/excisional biopsy).

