8.2.4 Guidelines for Management of Potential Adverse Events associated with Cabozantinib

Subjects will be monitored for AEs from the time of signing informed consent through their last follow-up visit (30 days after the date of the last dose of cabozantinib treatment.) Subjects will be instructed to notify their physician immediately at the onset of any AE. Seriousness, severity grade, and relationship to study treatment of AEs will be determined by the investigator. AE severity will be graded by the investigator in accordance with CTCAE v.4.0. Management of severe or intolerable adverse reactions may require temporary dose reduction and/or interruption for cabozantinib.

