10 SAFETY

10.1 Adverse Events and Laboratory Abnormalities

10.1.1 Adverse Events (AEs)

An AE is any untoward medical occurrence in a patient or clinical trial subject administered a medicinal product and which does not necessarily have a causal relationship with this treatment. An adverse event can therefore be any unfavorable and unintended sign (e.g. an abnormal laboratory finding), symptom, or disease temporarily associated with the use of a medicinal product, whether or not considered related to the medicinal product. An adverse event can arise from any use of the drug (e.g. off-label use, use in combination with another drug) and with any route of administration, formulation, or dose, including an overdose. This definition also includes AEs associated with medication errors and uses of the investigational product outside what is in the protocol, including misuse and abuse. Pre-existing medical conditions that worsen during the study should be recorded as AEs. Abnormal laboratory values, ECG findings, or vital signs are to be recorded as AEs if they meet the criteria described in this protocol. All untoward events that occur after informed consent through 30 days after the decision to discontinue study treatment (or the date the subject is deemed to be a screen failure) are to be recorded by the investigational site. This requirement includes AEs from unscheduled as well as scheduled visits and includes the new onset of or increase in pain during this period.

Adverse event terms recorded on the CRFs will be mapped to preferred terms using the Medical Dictionary for Regulatory Activities (MedDRA). Seriousness, severity grade, and relationship to study treatment will be assessed by the investigator. Severity grade will be defined by the current version of the National Cancer Institute (NCI)-Common Terminology Criteria for Adverse Events (CTCAE).

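### Subjects who stop all study drugs without progression have no scheduled 30-day adverse event check, although the protocol's safety rules require 30-day recording and status for everyone

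*Combined protocol and SAP*

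**What the plan says.** Section 7.3 asks subjects to return about 30 days after their last dose "to complete end-of-study assessments if they progressed on study while still on active treatment". If they are already off treatment when they progress, "then the end of study assessments may occur anytime within 30 days of documented disease progression". That second visit is anchored to progression and not to the last dose.

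Table 7-1 in Section 7.2 follows the same logic. The 30-day visit stands in the progression column. The column "Off treatment but not progressed" has visits every 12 weeks with a window of 4 weeks either way. It ticks concomitant medications, physical exam, vital signs, ECOG status, weight and labs, but not the AE assessment.

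The safety sections are wider. Section 10.1.1 requires recording of all untoward events "through 30 days after the decision to discontinue study treatment", whatever the reason for stopping and from unscheduled as well as scheduled visits. Section 10.2.4 requires the status of continuing AEs at that same 30-day point. Section 8.2.4 refers to a last follow-up visit "30 days after the date of the last dose of cabozantinib treatment", with no progression condition.

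On grading, Section 8.2.4 states that "AE severity will be graded by the investigator in accordance with CTCAE v.4.0", whereas Section 10.1.1 refers to whichever CTCAE version is current.

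**The concern.** Subjects can leave all study treatment without progression by several routes: toxicity, their own choice, the optional stop after 1 year in response, and completion of 2 years. None of these triggers the 30-day visit as Section 7.3 and Table 7-1 are written. Section 7.3 also ties additional AE follow-up to events still ongoing at that visit, which these subjects do not have.

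The rate of all-grade and grade 3-5 AEs is a secondary endpoint (Section 4.0). If the AE question is put at about 30 days to subjects who progressed on treatment, but not to those who stopped for other reasons, ascertainment differs by reason for stopping. The period matters clinically: the steroid tapers described in Sections 8.3.6 and 8.4.6 run 4 to 6 weeks, so a subject who stopped for an immune event may be tapering through all of it.

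**Working it through.** **1. Schedule against rule, by type of subject**

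| Subject | Contact scheduled by Section 7.3 and Table 7-1 | AE row ticked? | 30-day recording and status required (10.1.1, 10.2.4)? |
|---|---|---|---|
| Progresses on treatment | About 30 days after last dose | Yes | Yes |
| Stops all drugs, no progression | Every 12 weeks, 4 weeks either way | No | Yes |
| Off treatment, progresses later | Within 30 days of progression | Yes, but timed from progression | Yes, timed from stopping |
| Stops one drug class only (8.5) | Remains on the treatment schedule | Yes | Yes, once all treatment stops |

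The second row is the gap. The third row is the same subject later on. The blank does not look like a shifted table row, because neighbouring rows (physical exam, vital signs, labs) fill the same column.

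**2. Timing**

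Assumption: the 12-weekly visits and the 30-day window both run from the day treatment stops. Table 7-1 gives no anchor for the visits.

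- Earliest first visit: (12 − 4) × 7 = 56 days; 56 − 30 = 26 days after the window closes.
- Nominal first visit: 12 × 7 = 84 days; 84 − 30 = 54 days after.
- Latest first visit: (12 + 4) × 7 = 112 days; 112 − 30 = 82 days after.

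On this reading no scheduled contact falls inside the window. If the decision to stop comes later than the last dose, the two clocks separate and an early visit could fall inside a window counted from the decision. That is one reason to fix the anchor.

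**3. How far the anchors can differ**

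Section 7.3 counts from the last dose of study drug, Section 8.2.4 from the last cabozantinib dose, and Sections 10.1.1, 10.1.4 and 10.2.4 from the decision to discontinue. The cabozantinib dose-modification text in Section 8.2 allows a hold of up to 6 weeks for related AEs before discontinuation is called for. With a decision at 6 × 7 = 42 days after the last cabozantinib dose, one window closes at day 30 and the other at day 42 + 30 = 72.

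**4. How many subjects (illustration only)**

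The inputs are discontinuation rates for treatment-related AEs quoted in the protocol and the planned enrolment of 27.

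- Phase 1 triplet (Section 3.5): 27 × 2/18 = 3.0.
- Nivolumab/ipilimumab in CheckMate 067 (Table 3-1): 27 × 123/313 = 10.6, or about 11.

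This is an upper-type range for toxicity stops. It counts every discontinuation as a stop of all drugs, although Section 8.5 lets the other class continue, and it ignores subjects who also progress. The 39% (123/313) came from the regimen with the higher ipilimumab dose; Section 3.3 reports fewer treatment-related grade 3-4 events with the dose levels used here (34% against 48%). Stops by choice, in response or at 2 years are not included, and the documents give no rate for them.

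The number of events missed cannot be computed from the documents.

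**The case against.** The strongest reply is that AE capture does not depend on the visit table. Section 10.1.1 binds every subject and covers unscheduled contacts. Section 10.1.4 requires related SAEs to be reported even beyond 30 days. Section 10.2.4 requires related SAEs, and related AEs that led to discontinuation, to be followed to resolution or stability if still ongoing at 30 days. Laboratory changes that alter management must be recorded as AEs (Sections 7.4 and 10.2.1), and Table 8-10 sets frequent liver tests after hepatotoxicity. Section 7.2 also calls for more frequent assessments when clinically indicated.

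All of this stands, and it rules out two stronger readings. A reader might infer that subjects who stop for toxicity have no planned safety assessment; in fact exams and labs continue every 12 weeks, and the event that caused the stop is already recorded and followed. A reader might also infer that late immune events are left to chance; for serious related events Section 10.1.4 says otherwise.

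The reply does not close the gap. Sections 10.1.1 and 10.2.4 say what must be recorded, while the schedule tells a site when to ask. A new non-serious event in the month after stopping, in a subject with no visit due, depends on the subject reporting it or on an unscheduled contact.

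It is also fair to say that Section 8.2.4 is cabozantinib guidance, so it does not end study-wide AE recording when nivolumab continues alone; Section 10.1.1 governs. What remains there is a difference in anchors that needs reconciling.

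**Conclusion.** The concern holds as an inconsistency between the visit schedule and the protocol's own safety rules. For subjects who stop all study drugs without progression, Section 7.3 and Table 7-1 schedule no contact that delivers the 30-day AE recording and status. The timing result (first visit 26 to 82 days after the window closes) rests on counting the visits and the window from the same stopping day.

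The consequence is a risk of incomplete and uneven ascertainment of new, mainly non-serious events in the 30 days after stopping. It is tempting to conclude that AE rates will be under-counted, and that each missed subject moves a rate by 1/27 = 3.7 points. The documents do not support this. No count of missed events can be derived, and the 3.7-point step applies only when the subject has no other qualifying event. A subject who stopped for toxicity already has a recorded AE, often one that counts in the overall grade 3-5 rate. Rates of individual event types are more exposed than the overall per-patient rates. The endpoint of discontinuation due to AEs is unaffected, since it is known when the drug is stopped.

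The 3 to 11 of 27 shows only that the path may not be rare. The CTCAE difference is a smaller matter of consistency, with no effect on any rate shown.

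**What to change.** - In Section 7.3 and Table 7-1, apply the 30-day post-treatment safety visit or contact, with AE assessment, to every subject who stops all study treatment, whatever the reason.
- Use one AE window anchor, tied to the last dose of any study drug, in Sections 7.3, 8.2.4, 10.1.1, 10.1.4 and 10.2.4.
- Name one CTCAE version for AE grading in Sections 8.2.4 and 10.1.1.

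Ticking AE assessment at the 12-weekly off-treatment visits is optional. It would not by itself close the gap, because those visits fall after the 30-day window on the reading above, and it would extend routine AE collection beyond the protocol's own window.

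The cost is protocol wording and one brief contact for each subject who stops without progression.

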7.4 Laboratory Assessments

Laboratory panels are composed of the following:

Hematology 
 • WBC count with differential (including at minimum: neutrophils, basophils, eosinophils, lymphocytes, monocytes) • hematocrit • platelet count • RBC count • hemoglobin 		
Serum chemistry 
 • albumin • ALP • amylase • ALT • AST • bicarbonate • BUN • chloride • creatinine • GGT • Glucose • calcium • lactate dehydrogenase • lipase • magnesium • phosphorus • potassium • sodium • total bilirubin • total protein 		
Urinalysis 
 • appearance • color • pH • specific gravity • ketones • protein • UPCr • glucose • bilirubin • nitrite • creatinine • urobilinogen • occult blood (microscopic examination of sediment will be performed only if the results of the urinalysis dipstick evaluation are positive or not available) 		
Other 
 • TSH, Free T4 • Pregnancy test (urine or serum) for women of child-bearing potential • Creatine Kinase (CK), if CK is abnormal then Troponin-I must be drawn • PT/INR or PTT • 24 hour urine collection for protein if elevated UPCr >1mg/mg (>113.1mg/mmol; refer to Table 8-7) 		

ALP, alkaline phosphatase; ALT, alanine aminotransferase; AST, aspartate aminotransferase; BUN, blood urea nitrogen; ESR, erythrocyte sedimentation rate ; GGT, γ -glutamyltransferase;

INR, International Normalized Ratio; PT, prothrombin time; PTT partial thromboplastin time; RBC, red blood cell; TSH, thyroid stimulating hormone; UPCR, urine protein/creatinine ratio; WBC, white blood cell.

Abnormalities in clinical laboratory tests that lead to a change in subject management (eg, dose delayed [withheld] or reduced, requirement for additional medication, treatment or monitoring) are considered clinically significant for the purposes of this study, and will be recorded on the Adverse Events Case Report Form (CRF). If laboratory values constitute part of an event that meets criteria defining it as serious, the event (and associated laboratory values) must be reported as an SAE.

7.5 Treatment Response Assessment

Only those subjects who have measurable disease present at baseline, have received at least one dose nivolumab, ipilimumab and cabozantinib, and had one on-treatment scan or progressed clinically will be considered evaluable for response. These subjects will have their response classified according to the definitions stated below. Those subjects that are not evaluable for response will be replaced. Immune-Modified Response Evaluation Criteria in Solid Tumors (imRECIST) will be used for the primary response assessment and for progression free survival determination [33]. Best overall response rate will be reported. Start of treatment will define the start date for calculations of PFS and OS.

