1.0 SYNOPSIS

TITLE	Phase II study of Nivolumab/Ipilimumab plus Cabozantinib in patients with unresectable advanced melanoma
SHORT TITLE	Nivolumab/Ipilimumab plus Cabozantinib in Advanced Melanoma
PHASE	II
OBJECTIVES	
Primary objective:
 
 1. To determine progression free survival (PFS) for nivolumab/ipilimumab plus cabozantinib in patients with unresectable advanced melanoma 
Secondary objectives:
 
 1. To determine the response rate of nivolumab/ipilimumab plus cabozantinib in patients with unresectable advanced melanoma 2. To determine the overall survival (OS) of patients with unresectable advanced melanoma treated with nivolumab/ipilimumab plus cabozantinib 3. To determine the safety profile of nivolumab/ipilimumab plus cabozantinib in patients with unresectable advanced melanoma 
Exploratory objectives:
 
 1. To determine associations between baseline tumor mutational burden (TMB), angiogenesis pathways, and immunophenotyping with clinical activity of nivolumab/ipilimumab plus cabozantinib in patients with unresectable advanced melanoma 2. To determine associations between baseline mutations in genes regulating anti-tumor immunity with tumor immunophenotype and clinical activity of nivolumab/ipilimumab plus cabozantinib in patients with unresectable advanced melanoma 3. To assess on treatment biopsy for evidence of increased immune infiltration, vascularization, and MHC expression to nivolumab/ipilimumab plus cabozantinib in patients with unresectable advanced melanoma
STUDY DESIGN	In this phase II advanced melanoma study, all patients will receive treatment with nivolumab/ipilimumab plus cabozantinib for a 12 week induction period followed by nivolumab plus cabozantinib maintenance to complete up to 2 years of therapy unless disease

	
progression, dose limiting toxicity, provider/patient decision or patient withdrawal of consent occurs. The primary endpoint is the one year PFS rate. Patients will have staging scans at baseline and every 12 weeks during the first 2 years on study. Safety evaluations including labs, EKG and history and physical will occur at each visit. Baseline tumor sample is required and on treatment biopsy will be optional of superficial tumor in the skin, subcutaneous tissue or lymph node that is palpable.

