4.0 STUDY OBJECTIVES AND ENDPOINTS

Primary Objective	Primary Endpoint
To determine PFS for nivolumab/ipilimumab plus cabozantinib in patients with unresectable advanced melanoma	To determine the 1 year PFS rate for nivolumab/ipilimumab plus cabozantinib in patients with unresectable advanced melanoma using imRECIST
Secondary Objectives	Secondary Endpoints
To determine the response rate of nivolumab/ipilimumab plus cabozantinib in patients with unresectable advanced melanoma	To determine the ORR by imRECIST of nivolumab/ipilimumab plus cabozantinib in patients with unresectable advanced melanoma
To determine the OS of patients with unresectable advanced melanoma treated with nivolumab/ipilimumab plus cabozantinib	To determine the median and 3 year OS rate of patients with unresectable advanced melanoma treated with nivolumab/ipilimumab plus cabozantinib
To determine the safety profile of nivolumab/ipilimumab plus cabozantinib in	To determine the rate of all grade and grade 3-5 adverse events (treatment emergent and treatment related)

[figure not shown]
patients with unresectable advanced melanoma	
To determine the tolerability of nivolumab/ipilimumab plus cabozantinib in patients with unresectable advanced melanoma	To determine the rate of discontinuation of study drug(s) due to adverse events
Exploratory Objectives	
To determine associations between baseline tumor mutational burden (TMB), angiogenesis pathways, and immunophenotyping with clinical activity of nivolumab/ipilimumab plus cabozantinib in patients with unresectable advanced melanoma	To analyze molecular profiles based on whole exome sequencing (WES), PD-L1 immunohistochemistry and RNAseq from baseline tumors and correlate to ORR, PFS, and OS in patients with unresectable advanced melanoma treated with nivolumab/ipilimumab plus cabozantinib
To determine associations between baseline mutations in genes regulating anti-tumor immunity with tumor immunophenotype and clinical activity of nivolumab/ipilimumab plus cabozantinib in patients with unresectable advanced melanoma	To determine if loss of critical immune genes (such as IFN receptor and MHC) are associated with a low IFN gamma gene expression profile and impact on baseline tumors and correlate to ORR, PFS, and OS in patients with unresectable advanced melanoma treated with nivolumab/ipilimumab plus cabozantinib

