If the subject is unable to have a study assessment taken within the defined time window due to an event outside of his or her control (eg, clinic closure, personal emergency, inclement weather, vacation), the assessment should be performed as close as possible to the required schedule. Regular tumor assessments should be performed in accordance to the guidelines in [Section 7.4] to determine if PD is present.

The Treatment Period ends when a subject receives his or her last dose of study treatment; the subject then enters the Post-Treatment Period.

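### The ORR denominator implied by Section 7.5 leaves out treated subjects with no on-treatment scan or clinical progression, so ORR is too high if they respond less often than those kept

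*Combined protocol and SAP*

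**What the plan says.** Section 4.0 lists response rate as the first secondary endpoint: "To determine the ORR by imRECIST of nivolumab/ipilimumab plus cabozantinib in patients with unresectable advanced melanoma". It names no denominator.

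Section 7.5 sets the evaluable set. The conditions before and at dosing are: "Only those subjects who have measurable disease present at baseline, have received at least one dose nivolumab, ipilimumab and cabozantinib". The post-baseline condition is that the subject "had one on-treatment scan or progressed clinically will be considered evaluable for response". Two consequences are then stated: "These subjects will have their response classified according to the definitions stated below", and "Those subjects that are not evaluable for response will be replaced". The same paragraph adds: "Best overall response rate will be reported".

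On timing, the Synopsis says "Patients will have staging scans at baseline and every 12 weeks during the first 2 years on study", and Table 7-1 puts the first post-baseline imaging at week 13. Section 7.2 says "The Treatment Period ends when a subject receives his or her last dose of study treatment". Table 7-1 also schedules 12-weekly imaging for subjects who are off treatment and have not progressed. The text after Table 7-2 in Section 7.5.7 counts best overall response from the start of treatment until progression, recurrence or non-protocol therapy, which is not the same as until the last dose.

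Section 11 plans the 1-year PFS test in detail. For response it gives no denominator, no all-treated set, and no rule for treated subjects who were never assessed. It describes the analyses beyond PFS and OS as descriptive and exploratory.

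**The concern.** Measurable disease at baseline is a pre-treatment condition and does no harm as a filter; it is also an inclusion criterion. Receiving all three drugs and reaching an on-treatment scan depend on what happens after enrolment. A rate restricted in that way describes the subjects who got far enough to be assessed, not those who started the regimen.

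The subjects at risk of being lost are those who die before week 13 without recorded progression, those who leave the study entirely before any scan, and those who never receive one of the drugs. Under Section 7.5 they are neither classified nor kept: they are replaced. Some would still count in the Section 4.0 tolerability endpoint, as discontinuations for adverse events, while having no place in ORR.

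This matters more in a single-arm trial, because no concurrent arm is subject to the same exclusions. Section 2.0 hypothesizes greater activity than historical nivolumab/ipilimumab, and Section 3.3 quotes 57.6% for that regimen, so readers will set the reported ORR beside published rates. Toxicity on the triplet is not negligible: Section 3.5 reports grade 3-4 events in 13 of 18 subjects in the phase 1 study.

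**Working it through.** **The plan's own figures.** The plan states no sample size, precision or denominator for ORR. The numbers 23 and 27 come from the PFS design in Section 11: continue if at least 8 of 14 subjects are progression free, reject if at least 16 of 23 are. Exact binomial calculation gives alpha 0.0462 at a rate of 50% and power 0.8016 at 75%, in line with the stated 0.05 and 0.80. For 15% dropout, 23 / 0.85 = 27.06 and 23 × 1.15 = 26.45, so the stated ceiling of 27 is reasonable. That leaves 27 − 23 = 4 subjects as the dropout allowance.

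**Direction.** Let r be the responders among e evaluable subjects, and k the responders among m treated subjects who are excluded.

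- Evaluable-only ORR = r / e
- All-treated ORR = (r + k) / (e + m)
- The first exceeds the second exactly when k / m < r / e.

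So the evaluable-only rate is too high if the excluded subjects respond less often than those kept. If none of them responds (k = 0), this holds for any r > 0 and m > 0.

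**Size, with k = 0.** Take e = 23 and r = 13, so ORR is 13/23 = 56.5%, close to the 57.6% in Section 3.3. The number excluded, m, is an assumption.

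| Excluded, m | All-treated ORR | Gap from 56.5% (points) |
|---|---|---|
| 1 | 13/24 = 54.2% | 2.4 |
| 2 | 13/25 = 52.0% | 4.5 |
| 3 | 13/26 = 50.0% | 6.5 |
| 4 | 13/27 = 48.1% | 8.4 |

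The Clopper-Pearson 95% intervals are 34.5% to 76.8% for 13/23 and 28.7% to 68.1% for 13/27. With m = 4, the gap runs from 5.2 points at 8 responders (34.8% against 29.6%) to 10.3 points at 16 responders (69.6% against 59.3%).

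**Sensitivity to k.** With r = 13 and m = 4, the two rates are equal at k = 4 × 13/23 = 2.26. If 2 of the 4 excluded subjects responded, the all-treated ORR is 15/27 = 55.6%, nearly the same as 56.5%. If 3 responded it is 16/27 = 59.3%, and the bias is reversed.

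**Can an excluded subject be a responder?** Read literally, yes. Section 7.2 ends the treatment period at the last dose, so a scan taken after an early stop is not on treatment. A subject who stopped for toxicity and responded on a scheduled off-treatment scan would then fail the Section 7.5 condition, yet Section 7.5.7 would count the response. The two sections need to be reconciled.

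**The case against.** Four points can be made against this.

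1. *Section 11 does not state an evaluable-only denominator.* True: it is inferred from Section 7.5. But Section 7.5 says who is classified and that the rest are replaced, and nothing elsewhere restores them. The inference is the natural one.

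2. *Few subjects are affected.* Clinical progressors stay in. Section 8.5 lets a subject who stops one drug class continue the other, and so still reach the week 13 scan on treatment. Sections 8.3.6, 8.4.6 and 8.5 allow scans to be done earlier at the investigator's discretion when induction is delayed. In the phase 1 triplet study, the 2 of 18 discontinuations for treatment-related events came in maintenance (Section 3.5). All of this stands. It limits the likely size but leaves the rule as it is.

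3. *The direction is not guaranteed.* This also stands. A reader might infer that everyone who stops for toxicity in the first 12 weeks is a non-responder removed from the rate, so that the regimen looks more active because it is less tolerable. The documents do not support that: off-treatment scans are scheduled, and responses count until progression or non-protocol therapy.

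4. *Nothing depends on ORR.* Section 11 sets no ORR null, threshold or test, and at 23 subjects the confidence interval is far wider than the gap. This limits the severity. It does not make the denominator right, since a wide interval around a selected rate does not show the selection.

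**Conclusion.** The concern holds in this form: the ORR implied by Section 7.5 is conditional on events after treatment starts, and it exceeds an all-treated ORR whenever the excluded subjects respond less often than those kept. At 13 responders among 23, the excess is 2.4 to 8.4 points for 1 to 4 excluded subjects, assuming all were treated and none responded. The documents give no rate of non-evaluability, so the number excluded is an assumption, and 4 is an upper case.

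Two stronger readings should be avoided. A reader might take the plan's 15% as the share lost from ORR and compute 57.6 / 0.85 = 67.8%. That 15% is dropout over the whole study, set for a 1-year endpoint; a subject lost after the first scan is still evaluable for response, and 27 is an enrolment ceiling, not a count of treated subjects. A reader might also infer that the plan tests ORR against 57.6%; that figure is background in Section 3.3, and no formal comparison is planned.

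ORR is secondary and descriptive, so this denominator does not affect the alpha or power of the primary test. The change should be made, but it does not threaten the design.

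**What to change.** In Sections 7.5 and 11, state that:

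- ORR is confirmed CR plus PR divided by all subjects who received any study treatment.
- Any scan before progression or non-protocol therapy counts, whether on or off treatment, in line with Section 7.5.7.
- Subjects with no post-baseline assessment count as non-responders.
- The evaluable-subject ORR is reported alongside as a labelled sensitivity figure, with the number excluded and the reasons.

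This costs a few sentences and needs no extra subjects, visits or data. The downside is that the headline ORR may be slightly lower. The change is needed whatever is decided about replacement for the PFS test, although one definition of analysis populations could cover both.
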